2.2.1.1 MINIMIZATION OF POTENTIAL RISKS

These risks are mitigated by utilizing qualified clinical Investigators who have training and are experienced in subdermal Renuvion procedures. In addition, risks are mitigated by including only those subjects that meet the study eligibility criteria.

2.2.2 POTENTIAL BENEFITS

A possible benefit of using the Renuvion APR device in the lower eyelid area is the potential for improvement in the appearance of lax tissue in the lower eyelid region utilizing a minimally invasive technique.

Apyx Medical Corporation

Protocol Number: APX-22-04-GR

Effective Date: October 2, 2023

Revision No: 04

Title: A Post-Market Study in Greece of a Minimally Invasive Lower Eyelid Treatment Utilizing the Renuvion System Clinical Trial Protocol

3. STUDY PURPOSE

The purpose of this study is to evaluate the use of the Renuvion APR System as a minimally invasive lower eyelid procedure.

4. STUDY DESIGN AND ENDPOINTS

4.1 DESCRIPTION OF THE STUDY DESIGN

This is a prospective, multi-center, non-randomized, single-arm study of up to 16 subjects treated with the Renuvion APR System. Subjects will receive treatment with the Renuvion APR System in the lower periorbital area on both sides of the face.

At baseline, images will be taken utilizing the site's camera system. Baseline images will be used as comparator images for follow-up images for Independent Photographic Reviewer evaluation and subject/investigator assessments.

The treatment area will be tumesced with 20 - 25ml of fluid on each side of the periorbital area.

The treatment of the periorbital area will be accessed from an incision placed in the crease of the lower lid. Two incisions will be placed in both the medial and lateral crease of the lower lid. Treatment will be performed through one incision and the second incision will be used to allow for adequate venting of helium gas. Care will be taken to undermine the tissue and to ensure the incisions communicate with each other to allow adequate venting. An optional third lower lid incision may be made as needed. The treatment plane will be above the orbicularis muscle. The treatment settings will be 60-70% Power, 1 LPM, and 3 Passes. Procedure data and adverse events will be captured.

Follow-up will occur 1 day, 3 days, 7 days, 30 days, 90 days, and 180 days post-procedure; images will be taken at all visits. Investigator/subjects assessments will be completed at D30, D90, and D180 visits. Subjects may also be seen back for follow-up at the investigator's discretion.

4.2 DURATION OF STUDY

Recruitment for this study may take approximately four months. Following the treatment visit, subjects will be followed for a total duration of 180-days, after which, data will be analyzed. Therefore, the anticipated total duration of the study is approximately twelve months.

4.3 STUDY ENDPOINTS

4.3.1 PRIMARY EFFECTIVENESS ENDPOINT

Improvement in the lower eyelid area as determined by a masked, qualitative assessment of photographs at 180-days post-treatment compared to baseline. Improvement based on 2D photographs taken at all visits using the site's photography system.

Three experienced, blinded independent photographic reviewers (IPR) will perform a qualitative analysis/review of the pre-treatment and post-treatment sets of images of each subject in a blinded and randomized order. Each blinded reviewer will choose which image is the post-treatment image. Success will be correct post-treatment image

 Apyx Medical Corporation	
Protocol Number: APX-22-04-GR	Effective Date: October 2, 2023 Revision No: 04
Title: A Post-Market Study in Greece of a Minimally Invasive Lower Eyelid Treatment Utilizing the Renuvion System Clinical Trial Protocol	

selection by at least 2 of the 3 reviewers. The percentage of subjects with a correct post-treatment image selection will be calculated.

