Primary Outcome Measures:	Improvement in the lower eyelid area as determined by a masked, qualitative assessment of photographs at 180-days post-treatment compared to baseline. Improvement will be assessed based on photographs taken at all visits using the site's 2D camera system.

Apyx Medical Corporation

Protocol Number: APX-22-04-GR

Effective Date: October 2, 2023

Revision No: 04

Title: A Post-Market Study in Greece of a Minimally Invasive Lower Eyelid Treatment Utilizing the Renuvion System Clinical Trial Protocol

Secondary Outcome Measures:	
1. Improvement in the lower eyelid area as determined by a masked, qualitative assessment of photographs at 90-days post-treatment compared to baseline.2. Analysis of change from baseline to D30, D90, & D180 in Snap-back Test Grade (Bashour¹⁴).3. Analysis of change from baseline to D30, D90, & D180 in Medial Canthal Laxity Test Grade (Bashour¹⁴).4. Analysis of change from baseline to D30, D90, & D180 in Lateral Canthal Laxity Test Grace (Bashour¹⁴).5. The Principal Investigator will complete a GAIS¹³ assessing overall aesthetic improvement at day 30, 90, and 180 post-treatment.6. The subject will complete a GAIS¹³ assessing overall aesthetic improvement at day 30, 90, and 180 post-treatment.7. The subject will complete a patient satisfaction questionnaire at the 180-day follow-up visit.8. During study treatment, the subject's pain levels will be monitored using the 11-point Numeric Rating Scale (NRS)²⁰. The average pain score for the entire region treated will be recorded. Pain scores will be recorded at all follow-up visits.
Safety Variables:	
▪ Prior to treatment, the subject's medical history will be reviewed, a urine pregnancy test will be performed (if applicable), and a physical examination will be conducted.▪ Following study treatment and at each subsequent visit, the subject will be queried about adverse events, expected treatment effects, and changes in concomitant medications, and the treatment area will be visually examined.
Study Duration:	The duration from when the study opens to enrollment until completion of data analyses is anticipated to be 12 months.

Apyx Medical Corporation

Protocol Number: APX-22-04-GR

Effective Date: October 2, 2023

Revision No: 04

Title: A Post-Market Study in Greece of a Minimally Invasive Lower Eyelid Treatment Utilizing the Renuvion System Clinical Trial Protocol

TABLE OF CONTENTS

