4.3.3 ADDITIONAL OUTCOME MEASURES

1. Improvement in the lower eyelid area as determined by a masked, qualitative assessment of photographs at 90-days post-treatment compared to baseline.
2. Analysis of change from baseline to D30, D90, & D180 in Snap-back Test Grade (Bashour¹⁴).
3. Analysis of change from baseline to D30, D90, & D180 in Medial Canthal Laxity Test Grade (Bashour¹⁴).
4. Analysis of change from baseline to D30, D90, & D180 in Lateral Canthal Laxity Test Grace (Bashour¹⁴).
5. The investigator will complete a GAIS¹³ assessing overall aesthetic improvement in the treatment area at day 30, 90, and 180 post-treatment.
6. The subject will complete a GAIS¹³ assessing overall aesthetic improvement in the treatment area at day 30, 90, and 180 post-treatment.
7. The subject will complete a Patient Satisfaction Questionnaire (PSQ) at the 180-day follow-up visit.
8. During study treatment, the subject's pain levels will be monitored using the 11-point Numeric Rating Scale (NRS)²⁰. The average pain score for the entire region treated will be recorded. Pain scores will be recorded at all follow-up visits.

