4.3.4.1.1 INDEPENDENT PHOTOGRAPHIC ASSESSMENTS

Three experienced, blinded photographic reviewers will perform a qualitative analysis/review of the pre-treatment and post-treatment sets of images of each subject in a blinded and randomized order. Each

Apyx Medical Corporation

Protocol Number: APX-22-04-GR

Effective Date: October 2, 2023

Revision No: 04

Title: A Post-Market Study in Greece of a Minimally Invasive Lower Eyelid Treatment Utilizing the Renuvion System Clinical Trial Protocol

blinded reviewer will choose which image is the post-treatment image. Success will be correct post-treatment image selection by at least 2 out of 3 reviewers. The percentage of subjects with a correct post-treatment image selection will be calculated.

Assessment of each subject's baseline and follow-up images viewed simultaneously will be performed by the Independent Photographic Reviewers (IPR) who will be blinded to the study subject's visit (baseline and follow-up visit). Each IPR will view each subject's randomized pre-treatment and post-treatment images and assess which set of images represent the subject's post-treatment images. Each photograph will have a unique identification number, but the sets of images will not be arranged in any specific order (i.e., randomized order). The Sponsor will prepare and administer the IPR.

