4.3.4.1.2 INDEPENDENT PHOTOGRAPHIC REVIEW EVALUATION PROCESS

Each blinded assessor will be provided with identical photos to be assessed. The pre-treatment and post-treatment photos will be consistent in lighting, subject positioning, and focus. Each photo's visit interval, i.e., pre-treatment and post-treatment, will NOT be marked. The images placement (right or left) will be randomly ordered for pre-treatment and post-treatment images. Images for each subject will be grouped together into one set with all pre-treatment and post-treatment images in the same location (right/left) for the subject set.

Each blinded assessor will conduct their assessment independently with no input from another blinded assessor.

Each blinded assessor compares the Left and Right photo for change that may be striking (substantial and immediately noticeable), readily apparent but modest in nature, or slight and subtle in nature that may require close examination. Assessors should look through each view and assess change. Enough time should be allowed to do this for each subject, so the assessments are not rushed.

The assessor chooses which photo they believe to be the post-treatment photo (i.e., Left photo or Right photo) once all images in the subject set have been reviewed.

Post-Analysis Coding of Masked Assessment:

- If the assessor incorrectly chooses the post-treatment photo, this will be coded as an "Incorrect post-treatment selection".
- If the assessor correctly chooses the post-treatment photo, this will be coded as a "Correct post-treatment selection".
- Success will be determined by correct identification of post-treatment photographs by at least two out of three blinded, independent reviewers.

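### The masked primary endpoint is called improvement, but it counts correct identification of the post-treatment photo, whichever way the lid changed

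*Combined protocol and SAP*

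**What the plan says.** The Protocol Synopsis and section 4.3.1 both name the primary effectiveness endpoint as "Improvement in the lower eyelid area as determined by a masked, qualitative assessment of photographs at 180-days post-treatment compared to baseline". Section 4.3.3, item 1, uses the same label for a secondary endpoint at D90: "Improvement in the lower eyelid area as determined by a masked, qualitative assessment of photographs at 90-days post-treatment compared to baseline".

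The scoring rule in 4.3.1 is "Each blinded reviewer will choose which image is the post-treatment image", and 4.3.4.1.1 adds "Success will be correct post-treatment image selection by at least 2 out of 3 reviewers". Section 4.3.4.1.2 repeats it: "Success will be determined by correct identification of post-treatment photographs by at least two out of three blinded, independent reviewers". The reported statistic is the percentage of subjects with a correct selection.

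On the task itself, 4.3.4.1.2 states "Each blinded assessor compares the Left and Right photo for change that may be striking" and goes on to cover modest and subtle change. The answer is Left or Right, coded only as correct or incorrect. On layout: "The images placement (right or left) will be randomly ordered for pre-treatment and post-treatment images". The training outline in 4.3.4.1.3 directs attention to changes in laxity, fine lines and overall appearance, without a direction.

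Section 10.1 plans descriptive statistics only, and 10.2 sets up to 16 treated subjects. No chance rate or benchmark is given.

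**The concern.** Telling which photo was taken after treatment is not the same as judging that it looks better. Under the written rule a laxer lid is as usable a cue as a tighter one, and so is a scar, a pigment change or an asymmetry. Section 2.2.1 lists all three as possible risks, without rates. The incisions lie in the lower-lid crease, inside the photographed area, and the documents do not say whether they are visible at D180.

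The forced choice adds a second problem: a subject with no visible change still has an even chance of being a success.

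The percentage therefore pools improved subjects, subjects recognised for other reasons, and lucky guesses, and no masked data separate them. In a single-arm study this percentage is the main effectiveness result, and its label invites readers to take it as the share of subjects who improved.

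**Working it through.** The plan states no power, threshold or expected rate, so there is no figure to reproduce.

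**1. Label against rule.** The label is improvement (Synopsis, 4.3.1, 4.3.3). The rule is correct identification by 2 of 3 (4.3.1, 4.3.4.1.1, 4.3.4.1.2). No form field records better or worse. Section 4.3.3 has no separate D90 rule. Sections 4.3.4.1.1 and 4.3.4.1.2 describe the review generically for baseline against follow-up images, so I infer that D90 is scored the same way.

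**2. Is direction recovered elsewhere?** The GAIS (4.3.4.5) has three worse grades, but the investigator and the subject rate it knowing the visit. The laxity grades (4.3.4.2 to 4.3.4.4) are compared with baseline but are not described as masked. Neither enters the primary percentage. Cross-tabulating them with it would separate the groups only in part.

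**3. Chance floor.** If placement is random 1:1, the side a guessing majority picks is right with probability 0.5, however correlated the reviewers are. Expected successes: 16 × 0.5 = 8. With X ~ Bin(16, 0.5):
- P(X ≥ 12) = 0.038
- P(X ≥ 13) = 0.011
- Exact (Clopper-Pearson) 95% interval for 12/16 (75%): 47.6% to 92.7%
- Exact 95% interval for 13/16 (81.3%): 54.4% to 96.0%

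The tails are one-sided and the intervals two-sided. Both are given for scale, since the plan has no test.

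**4. Illustrations (all rates assumed).** Let x be the probability that one reviewer picks the post-treatment photo, and r the share of subjects on whom all three necessarily agree. Subject-level success is M(x, r) = r·x + (1 − r)·[3x²(1 − x) + x³]. At r = 0: M(0.1) = 0.028, M(0.7) = 0.784, M(0.9) = 0.972. At r = 1: M = x. M(0.5) = 0.5 for every r. Assume improved subjects have x = 0.9, unchanged subjects x = 0.5, and worsened subjects x = p, from 0.1 to 0.9.

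| Mix of 16 | True improvement | Plan reports, r = 0 | Plan reports, r = 1 |
|---|---|---|---|
| (1) 4 worse, 12 unchanged | 0% | 38.2% to 61.8% | 40.0% to 60.0% |
| (2) 4 better, 4 worse, 8 unchanged | 25% | 50.0% to 73.6% | 50.0% to 70.0% |
| (3) no change, neutral trace in 8, used with accuracy 0.7 or 0.9 | 0% | 64.2% or 73.6% | 60.0% or 70.0% |

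At r = 0:
- (1) 0.25·M(p) + 0.75·0.5, which is 0.007 + 0.375 to 0.243 + 0.375
- (2) 0.25·0.972 + 0.25·M(p) + 0.5·0.5
- (3) 0.5·M(a) + 0.5·0.5, with a = 0.7 or 0.9

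**5. The same mixes under a preference rating.** Let h be the share of ratings that simply favour the photo believed to be post-treatment. The per-reviewer probability that the post-treatment photo is rated better is (1 − h)·d + h·s. Here d = 0.9 if improved, 0.1 if worsened, and 0.25 if unchanged or trace-only (no difference used half the time). The term s is the pick probability from step 4.

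| Mix | h = 0, r = 0 [r = 1] | h = 0.5, r = 0 [r = 1] |
|---|---|---|
| (1) | 12.4% [21.2%] | 24.4% to 36.2% [30.6% to 40.6%] |
| (2) | 32.8% [37.5%] | 40.8% to 52.6% [43.8% to 53.8%] |
| (3) | 15.6% [25.0%] | 38.9% to 46.4% [42.5% to 47.5%] |

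At h = 1 the rating reproduces the plan's figures.

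**The case against.** The strongest reply is that the study is small, post-market and descriptive. It has no hypothesis or success threshold, so no formal decision can go wrong. The scoring rule is openly stated, and the statistic is described as a percentage with correct selection. That is true, and no error rate is affected. It does not rescue the label, because in an uncontrolled study readers will take the headline percentage for what it is called.

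A second reply is that reviewers will assume the post-treatment photo is the better one, so worsened subjects would tend to be coded incorrect. The documents do not instruct this. The training list is not exhaustive, so fuller material might. Even then the label fails: at p = 0.1, mix (1) gives 38.2% with nobody improved and mix (2) gives 50.0% with 25% improved.

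Third, the illustrations owe more to guessing than to direction. This stands. Replacing the four worsened subjects with unchanged ones gives 50% in mix (1) and 61.8% in mix (2) with independent reviewers. The effect of worsening alone is therefore 11.8 points either way, depending on p. Missing direction and the forced-choice floor are two separate defects of the same rule.

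Fourth, standardised views, lighting and reshoots (4.3.4.1, 4.3.4.1.2) limit photographic cues. They do, but they do nothing about scars or real worsening.

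**Conclusion.** The concern holds. The label and the scoring rule measure different things, and nothing else in the protocol supplies a masked measure of improvement. This follows from the text alone. The 50% chance rate needs only 1:1 random placement. The D90 point rests on the inference that the same review rule applies there.

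The net bias has no known size or sign: recognised worsening raises the percentage, and an assumption that post-treatment means better lowers it. The illustrated figures rest on assumed mixes and accuracies and show only what the rule permits. The endpoint should be corrected, because as written the plan would present detectability as improvement.

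**What to change.** Amend 4.3.1, 4.3.4.1.1 and 4.3.4.1.2 as follows, using the same image sets and the same three reviewers:
- First ask, still masked, which side shows the better lower-eyelid appearance: left, right or no difference. Lock that answer, then ask for the identification.
- Report as improved only subjects whose post-treatment photo is rated better by at least 2 of 3. Every other split counts as not improved.
- Also report how many subjects had the baseline photo preferred by at least 2 of 3.
- Report correct identification under its own name, beside the 50% chance rate.
- In 4.3.4.1.3, train reviewers to judge which side looks better on each feature.
- Do the same at D90, in place before the D90 interim analysis (10.1) if those photos are read then.

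The cost is one form item: at most 16 × 3 × 2 = 96 ratings, with no new photos, visits or readers, plus a protocol amendment with IRB approval (15.2). If the D90 photos have already been read, a repeat read is 16 × 3 = 48 ratings. The headline figure may be less favourable. The change reduces the bias without removing it, since a reviewer who recognises the post-treatment photo may still favour it.

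The minimum is to rename the endpoint as correct identification of the post-treatment photograph, state the 50% chance rate, and not report it as an improvement rate. That changes wording only, but still leaves the study without a masked measure of improvement.

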4.3.2 PRIMARY SAFETY ENDPOINT

The primary safety endpoint is an analysis of adverse events through the D180 post-treatment visit.

4.3.3 ADDITIONAL OUTCOME MEASURES

1. Improvement in the lower eyelid area as determined by a masked, qualitative assessment of photographs at 90-days post-treatment compared to baseline.
2. Analysis of change from baseline to D30, D90, & D180 in Snap-back Test Grade (Bashour¹⁴).
3. Analysis of change from baseline to D30, D90, & D180 in Medial Canthal Laxity Test Grade (Bashour¹⁴).
4. Analysis of change from baseline to D30, D90, & D180 in Lateral Canthal Laxity Test Grace (Bashour¹⁴).
5. The investigator will complete a GAIS¹³ assessing overall aesthetic improvement in the treatment area at day 30, 90, and 180 post-treatment.
6. The subject will complete a GAIS¹³ assessing overall aesthetic improvement in the treatment area at day 30, 90, and 180 post-treatment.
7. The subject will complete a Patient Satisfaction Questionnaire (PSQ) at the 180-day follow-up visit.
8. During study treatment, the subject's pain levels will be monitored using the 11-point Numeric Rating Scale (NRS)²⁰. The average pain score for the entire region treated will be recorded. Pain scores will be recorded at all follow-up visits.

4.3.4 EVALUATION TOOLS

The following evaluation tools will be used in this study:

4.3.4.1 2-DIMENTIONAL PHOTOGRAPHY

Two-dimensional (2D) photographic images will be captures utilizing the site's camera system. The same standardized photography views will be used throughout the study. Images will be captured as follows:

- With the subject's entire face freshly washed and clear of eye makeup. Permanent make-up tattoos, if any, will be noted in the Case Report Form.
- With no jewelry (eyebrow rings, nose rings, earrings, necklace, etc.).
- With the subject's eyes open.
- With no expression on the subject's face (smiling, smirking, etc.).
- Aligned to the Frankfurt Plane (see **Appendix C**).

Images will be monitored for quality to ensure standardized images and subject alignment between baseline and follow-up visits. A reshoot may be requested if images are poor photographic quality and/or changes in subject positioning or alignment. Study staff should review photos with particular care during each visit to ensure consistent alignment to prevent having to bring the subject back for a reshoot. If a reshoot is required, the reshoot should be taken within the visit window. Study staff should review Photography Result Reports (provided within 48 hours of image upload) for all images taken to check for reshoot requests.

Baseline images may be taken within 30 days prior to study treatment. Subject baseline photos are reviewed by Apyx staff prior to study treatment to ensure proper subject selection.

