5.1.3.1 SCREEN FAILURES

A screen failure subject is one from whom informed consent is obtained and is documented in writing (i.e., subject signs an Informed Consent Form), but who does not receive a study treatment because of failure to meet all of the eligibility criteria. Screen failure subjects will be included in the total number of subjects enrolled (i.e., all subjects consented), but not counted towards the total subjects treated.

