5.2 INCLUSION CRITERIA

Subjects must meet all of the following criteria for study enrollment:

- Male or female subjects, ages 18 – 75 years old.
- ASA Physical Status Classification System Class I and Class II subjects.
- Complaint of skin laxity or lines in the lower eyelid area.
- Understands and accepts the obligation not to undergo any other procedures or treatments in the areas to be treated during study participation.
- Absence of physical conditions unacceptable to the investigator.

Apyx Medical Corporation

Protocol Number: APX-22-04-GR

Effective Date: October 2, 2023

Revision No: 04

Title: A Post-Market Study in Greece of a Minimally Invasive Lower Eyelid Treatment Utilizing the Renuvion System Clinical Trial Protocol

- Females of childbearing potential who are sexually active must be willing to use an approved method of birth control during study participation.
- Willing and able to comply with protocol requirements, including study-required images/photos, assessments/measurements, and returning for follow-up visits.
- Willing to release rights for the use of study photos, including in publication.
- Able to read, understand, sign, and date the informed consent.
- Able to communicate with the site via video and/or photographs, in the event of a virtual follow-up visit.

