Study staff will contact (phone, text, email, video call at subject's preference) all subjects with ongoing Adverse Events at regular intervals. If the subject is unreachable by the preferred method of contact, another method of contact may be attempted.

Apyx Medical Corporation

Protocol Number: APX-22-04-GR

Effective Date: October 2, 2023

Revision No: 04

Title: A Post-Market Study in Greece of a Minimally Invasive Lower Eyelid Treatment Utilizing the Renuvion System Clinical Trial Protocol

TABLE 6: STUDY REQUIRED PROCEDURES

	Baseline/ Pre-Procedure Screening ¹	Procedure (Day 0)	1 Day	3 Days	7 Days	30 Days	90 Days	180 Days
			1 day	2-4 days	4-10 days	23-37 days	80-100 days	165-195 days
Informed Consent	X							
Assess Inclusion/Exclusion Criteria	X							
Urine Pregnancy Test ²	X	X						
Medical History	X							
General Physical Exam	X							
Review Medications	X	X	X	X	X	X	X	X
Visia Photographic Images ³	X ⁶	X ⁶		X	X	X	X	X
Numeric Rating Scale (11-point NRS)		X ⁴	X	X	X	X	X	X
Study Procedure		X						
Adverse Event Assessment		X	X	X	X	X	X	X
Laxity Assessments	X					X	X	X
Modified Global Aesthetic Improvement Scale (GAIS) ⁵						X	X	X
Subject Satisfaction Survey								X

¹ Pre-procedure Screening assessments to take place within 30 days prior to undergoing the procedure.² Up to two urine pregnancy tests must be obtained prior to study procedure for females with child-bearing potential (one at pre-procedure screening and one on the day of the procedure prior to the procedure).³Digital photographs will be taken and labeled according to Photography Instructions. Standard positioning and lighting will be used for all photographs.⁴ NRS pain score will be captured prior to study treatment and immediately (within 60 minutes) after procedure.⁵ To be completed by Investigator and study subject at day 30, 90, and 180 follow-up visits.⁶ Pre-procedure images may be taken if Baseline/Screening images are not considered acceptable by the quality review team, however if the Baseline/Screening image is acceptable by the quality review team, no additional pre-procedure image needs to be taken.

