7.3 STUDY SCHEDULE

7.3.1 SCREENING

- Obtain informed consent of potential participant verified by signature on study informed consent form.
- Verify all preliminary/screening inclusion/exclusion criteria are met.
- Perform screening photography (may be used as baseline images).

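### The baseline photograph that sponsor staff use to check subject selection, with no stated criterion, is normally also the comparator for the masked reads, which leaves the primary endpoint open to regression to the mean

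*Combined protocol and SAP*

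**What the plan says.** Section 4.3.4.1 (2-Dimensional Photography) describes two separate checks on the images. One concerns photographic quality and alignment, with reshoots on request. The other concerns who is treated: "Subject baseline photos are reviewed by Apyx staff prior to study treatment to ensure proper subject selection". No criterion, scale or severity threshold is given for this second check.

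Section 5.2 defines the treated condition only by the subject's own report: "Complaint of skin laxity or lines in the lower eyelid area". Section 5.3 gives the discretionary exclusion to the investigator.

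On the role of the image, section 4.1 says: "Baseline images will be used as comparator images for follow-up images for Independent Photographic Reviewer evaluation and subject/investigator assessments". The Screening list under Study Schedule allows screening photographs to serve as baseline. Table 6 footnote 6 provides for a new image only when the existing one is poor: "Pre-procedure images may be taken if Baseline/Screening images are not considered acceptable by the quality review team". Otherwise, "if the Baseline/Screening image is acceptable by the quality review team, no additional pre-procedure image needs to be taken".

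The primary endpoint (4.3.1) is a choice between the left and right image sets. A subject is a success if at least two of three masked readers pick the true post-treatment set. The design is single-arm (4.1), the analysis is descriptive (10.1), and up to 16 subjects are treated (10.2).

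**The concern.** How a lower eyelid looks in one photograph reflects a lasting part (laxity, lines) and a part particular to that day, such as swelling or fatigue. If subjects are accepted or declined partly on one image, the day-specific part of that image is selected too. A later image of the same untreated person will tend to move back towards that person's usual appearance. When the selecting image is also the baseline in the pair, this movement enters the comparison directly.

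The endpoint is sensitive to it. Readers have no option to record no change, and section 4.3.4.1.2 tells them that the difference may be slight. A small shift in average appearance can therefore move the proportion of correct picks. With no untreated arm, nothing in the design separates that shift from an effect of the device. The GAIS and the satisfaction survey also refer back to pre-treatment photographs, so the issue is not confined to the masked reads.

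**Working it through.** The documents give no null rate, target rate, alpha or power, so there is no stated figure to reproduce.

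**Chance level of the success rule.** If each reader guesses independently, P(at least 2 of 3 correct) = 3 × 0.5² × 0.5 + 0.5³ = 0.375 + 0.125 = 0.50. The expected count is 16 × 0.50 = 8, and P(at least 12 of 16) = 3.8%.

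**Model (all inputs are assumptions).** There is no treatment effect. X is apparent severity in the selecting image and Y is severity in a later image of the same untreated subject. Both are standard normal with correlation r, taken as 0.8 to 0.95. A fraction f of subjects is kept. Readers call the better-looking image post-treatment and, at first, have no noise of their own. A pick is then correct when D = X − Y > 0.

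**Closed form for keeping the worse-looking half.** Corr(X, D) = (1 − r)/√(2(1 − r)) = √((1 − r)/2), so P(D > 0 | X > 0) = 0.5 + asin(√((1 − r)/2))/π.

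- r = 0.80: 0.5 + asin(0.316)/π = 0.602
- r = 0.90: 0.5 + asin(0.224)/π = 0.572
- r = 0.95: 0.5 + asin(0.158)/π = 0.551

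**Other kept fractions (simulation), worse-looking subjects favoured.**

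| r | 50% kept | 75% kept | 90% kept |
|---|---|---|---|
| 0.80 | 0.602 | 0.554 | 0.524 |
| 0.90 | 0.572 | 0.538 | 0.517 |
| 0.95 | 0.551 | 0.527 | 0.512 |

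In 16 subjects the excess over chance runs from 16 × 0.012 = 0.2 to 16 × 0.102 = 1.6 successes. At the top of the range, P(at least 12 of 16) is about 17% instead of 3.8%. The plan sets no such threshold; 12 is only an illustration.

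**Reader noise.** With noise of SD 0.5 for each reader and half kept, the two-of-three rate is 0.590, 0.558 and 0.535 at r = 0.8, 0.9 and 0.95. That is about 1.5 points lower.

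**Outside this grid.** Stricter selection gives more: at r = 0.8 with the worst quarter kept, the rate is 66%.

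**Other directions of selection.**

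- Worst-looking 10% dropped: this mirrors the 90% column, so 1 − 0.524 = 0.476, 1 − 0.517 = 0.483 and 1 − 0.512 = 0.488.
- Milder half kept, r = 0.9: 1 − 0.572 = 0.428.
- Both 10% tails dropped: 0.50.

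**Effect of a separate comparator.** Suppose the comparator is a new image whose day-specific part is independent of the selecting image. Then, with no treatment effect, the comparator and the follow-up image are exchangeable given the selection. The rate returns to 0.50 whichever way staff selected.

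**The case against.** The strongest reply is that the text never says worse-looking subjects are preferred. Proper selection may simply mean checking the listed criteria, and photographs can bear on several of them: festoons, local skin disease, lesions in the treatment area, and perhaps the complaint itself. A review limited to these leaves the rate near 50%, and removing conspicuous cases pushes it slightly below. This stands. A reader might infer that the sponsor picks bad-looking lids and that the success rate is therefore inflated; the documents do not support that.

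A reader might also infer that this selection leaves no trace, because section 5.1.3.1 defines a screen failure as someone who "does not receive a study treatment because of failure to meet all of the eligibility criteria". That does not hold either. Under section 5.1 everyone who signs consent is enrolled and has an exit form. Section 11 lists screening logs as source documents, and section 14.2.1 requires an enrolment log. Consented but untreated subjects are therefore on record.

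Photographic noise is also limited by consistent lighting, fixed positioning, no make-up or expression, several views and reshoots. That supports high correlations, and hence the lower part of the range, but it does not remove day-to-day swelling or fatigue. Finally, the analysis is descriptive, so there is no formal threshold for the shift to cross. That is true, but the percentage will still be read against a chance level that the plan does not state.

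**Conclusion.** The concern holds as a vulnerability of the design; it does not demonstrate a bias. Three features combine: a selection review with no written criterion, reuse of the reviewed image as comparator, and an uncontrolled forced-choice endpoint.

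If worse-looking images are favoured, the no-effect rate of correct picks is about 51% to 60%, or 0.2 to 1.6 extra successes in 16. If the worst-looking 10% are dropped, it is about 48% to 49%. If only listed criteria are checked, it is near 50%. These figures rest on normality, correlations of 0.8 to 0.95, 50% to 90% kept and noise-free readers, none of which is in the documents. The top of the range requires half of the candidates to be turned away. Because the selection rule is unwritten, the plan gives no basis for choosing among these cases.

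**What to change.** Change Table 6 footnote 6 so that every subject has the standard image set taken on Day 0, before tumescence. Name that set as the baseline comparator for the D90 and D180 masked reads. Keep the quality-approved screening set as a fallback only when the Day 0 set fails quality review, and report how many subjects used it. This separates the selecting image from the comparator and works whichever way the selection ran.

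Costs and limits:

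- A few minutes of photography at a visit where Table 6 already allows images, and a short amendment.
- Some mixed comparators. Section 4.3.4.1 gives up to 48 hours for photography reports, so a poor Day 0 set may be found only after treatment, when it cannot be retaken.
- Little gain when screening and treatment fall on the same day, which section 7.1 permits, because both sets then share that day's appearance.
- Possibly a slightly lower observed success rate.
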